6.6 EFFICACY ANALYSES

All efficacy analyses will be performed on the safety-evaluable population, which is defined as patients who receive any amount of study drug.

6.6.1 Primary Efficacy Endpoint

The primary endpoints for efficacy are ORR and PFS. For patients with measurable disease or patients with neuroblastoma who have evaluable disease at baseline, an objective response is defined as a complete or partial response on two consecutive occasions ≥ 4 weeks apart, as determined by the investigator using RECIST v1.1 for patients with solid tumors (see [Appendix 6](#)), *mINRC* for patients with neuroblastoma (see [Appendix 3](#)), Revised Response Criteria for Malignant Lymphoma for patients with Hodgkin's lymphoma or non-Hodgkin's lymphoma (see [Appendix 4](#)), and *RANO criteria* (see [Appendix 11](#)) for patients with ATRT.

For patients with non-measurable but evaluable disease at baseline (except *patients with neuroblastoma*), an objective response is defined as a complete response on two consecutive occasions ≥ 4 weeks apart, as determined by the investigator using RECIST v1.1 for patients with solid tumors (see [Appendix 6](#)), Revised Response Criteria for Malignant Lymphoma for patients with Hodgkin's lymphoma or non-Hodgkin's lymphoma (see [Appendix 4](#)), and *RANO criteria* (see [Appendix 11](#)) for patients with ATRT.

ORR is the percentage of patients who are determined to have an objective response. Patients with no post-baseline tumor assessments will be counted as non-responders. ORR and corresponding 95% exact CI using the Blyth–Still–Casella method will be summarized overall and by tumor type cohort (except for the osteosarcoma tumor type cohort).

CBR is defined as objective response or stable disease for at least 6 months, as determined by RECIST v1.1 for patients with osteosarcoma (see [Appendix 6](#)). CBRR is the percentage of patients who are determined to have a CBR. Patients with no post-baseline tumor assessments will be counted as not having CBR. CBRR and corresponding 95% CI will be summarized for the osteosarcoma tumor type cohort only.

PFS is defined as the time from initiation of study drug to the first documented occurrence of disease progression, as determined by the investigator using RECIST v1.1 for patients with solid tumors (see [Appendix 6](#)), *mINRC* for patients with neuroblastoma (see [Appendix 3](#)), Revised Response Criteria for Malignant Lymphoma for patients with Hodgkin's lymphoma or non-Hodgkin's lymphoma (see [Appendix 4](#)), and *RANO criteria* (see [Appendix 11](#)) for patients with ATRT, or death from any cause, whichever occurs first. Data for patients without progressive disease or death will be censored at the date of the last tumor assessment at which the patient was known to be progression-free or, if no tumor assessment is performed after the baseline visit, at the date of initiation of study drug. The Kaplan-Meier approach will be used to estimate median PFS. The 95% CI of the median PFS will be estimated using the Brookmeyer

and Crowley method. Subgroup analysis of PFS by tumor type cohort will be conducted as appropriate.

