Patients with pediatric solid tumors, including Hodgkin's and non-Hodgkin's lymphoma, may be enrolled into the study (see Section 4.1 for patient inclusion and exclusion criteria). Each tumor type will be considered a distinct tumor type cohort. An initial response assessment will be performed after a minimum of 10 patients have been enrolled in a tumor type cohort and followed up for approximately 6 months, to determine whether further enrollment is needed within that tumor type cohort (cohort expansion) for additional response assessment. A minimum number of responders will be needed for cohort expansion and advancement to the additional response assessment (see [Table 3](#) for more details). Cohort expansion, including the number of patients needed for the additional response assessment, will also take into account practical considerations (e.g., enrollment feasibility), biomarker analysis, safety profiles, and any other relevant information. The maximum number of patients enrolled in any tumor cohort will be 40.

In addition to the planned efficacy analyses mentioned above, interim PK analyses will also be performed. An initial interim PK analysis will be conducted after the first 5 patients have completed Cycle 1, irrespective of age and tumor type cohort. An additional interim PK analysis will be conducted after 5 patients who are < 6 years old (if available) have completed Cycle 1. Following these analyses, dose modifications may be considered for all patients, if warranted, to match adult exposures and to ensure an optimal safety profile. After a minimum of 20 patients have completed Cycle 1, PK and safety analyses will also be conducted.

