6. STATISTICAL CONSIDERATIONS AND ANALYSIS PLAN

The study is an early-phase, multicenter, open-label, single-arm study designed to evaluate the safety, tolerability, pharmacokinetics, immunogenicity, and preliminary efficacy of atezolizumab in pediatric and young adult patients with solid tumors for which prior treatment has proven to be ineffective (i.e., relapsed or refractory disease) or intolerable and for whom there is no effective standard treatment available. The primary analysis will be conducted after the enrollment has been completed and all enrolled patients have been followed up for at least 6 months. A primary Clinical Study Report will be submitted to health authorities for information.

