6.1 DETERMINATION OF SAMPLE SIZE

No formal hypothesis testing is planned in this study.

A minimum of 40 patients will be enrolled in this study across all tumor types. In addition, at least two tumor type cohorts must enroll a minimum of 10 patients. To make a preliminary assessment of the efficacy of the study drug, two response assessments are planned: an initial response assessment and an additional response assessment. Taking into account historical control ORRs for each pediatric tumor type, the minimum number of patients in the initial response assessment and the minimum number of responders needed for cohort expansion and advancement to the additional response assessment were calculated and are presented by tumor type in [Table 3](#). Given the bony nature of osteosarcoma, responses in osteosarcomas do not always result in tumor shrinkage as the extracellular matrix produced by the tumor cells does not always disappear even when the cells die ([Benjamin RS 2015](#)). Thus, for osteosarcoma, CBR instead of objective response was considered in the response assessment. Patients with osteosarcoma are considered to have CBR if they have objective response or stable disease for at least 6 months, as determined by RECIST v1.1.

An initial response assessment will consider any available preclinical data in addition to any early efficacy or safety signals seen in the tumor type cohorts (enrollment may be closed while the response assessments are being conducted). The selection of expansion cohorts for additional response assessment, as well as the number of patients needed for the additional response assessment, will also take into account practical considerations (e.g., enrollment feasibility), biomarker analysis, safety profiles, and any other relevant information. The maximum number of patients per tumor type cohort will be 40. Similar consideration will be given to other rare pediatric tumor types that are enrolled in the study and not included in [Table 3](#).

Table 3 Sample Size and Responder Requirements for Initial Response Assessment

Disease (Relapsed/Refractory)	Historical Control Objective Response Rate (%)	Initial Response Assessment	
		Minimum No. of Patients Enrolled	Minimum No. of Responders Needed for Tumor Type Cohort Expansion
Hepatoblastoma	10%	10	2
Hodgkin's disease	60 ^a	14	10
Wilms tumor	10	10	2
Neuroblastoma	18	10	3
Non-Hodgkin's lymphoma	40 ^a	12	6
High-grade osteosarcoma	20 ^b	10	3
Rhabdomyosarcoma	10	10	2

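### Given expansion, a cohort's pooled ORR is biased upward on average, because the planned estimate and 95% CI ignore the first-stage responder gate

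*Combined protocol and SAP*

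**What the plan says.** Section 3.1 sets the gate: "A minimum number of responders will be needed for cohort expansion and advancement to the additional response assessment". Section 6.1 says that, taking historical response rates into account, "the minimum number of responders needed for cohort expansion and advancement to the additional response assessment were calculated". Table 3 lists the results in a column headed "Minimum No. of Responders Needed for Tumor Type Cohort Expansion":

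- 2 of 10 for the five tumor types with a 10% historical rate
- 3 of 10 for neuroblastoma (18%) and for osteosarcoma (20%, clinical benefit)
- 6 of 12 for non-Hodgkin's lymphoma (40%)
- 10 of 14 for Hodgkin's disease (60%)
- 1 of 6 for rhabdoid tumor and for ATRT (5%)

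The expansion size is left open. The choice of cohorts, "as well as the number of patients needed for the additional response assessment, will also take into account practical considerations", and the only fixed figure is the cap: "The maximum number of patients per tumor type cohort will be 40". Section 3.1.2 words the stopping rules permissively and lists exceptions, one of which extends a rare, slow-enrolling cohort on a positive efficacy signal.

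The analysis does not mention the gate. Section 6.6 states: "All efficacy analyses will be performed on the safety-evaluable population, which is defined as patients who receive any amount of study drug". Section 6 sets the timing: "The primary analysis will be conducted after the enrollment has been completed and all enrolled patients have been followed up for at least 6 months". Section 6.6.1 then gives the estimate and interval: "ORR and corresponding 95% exact CI using the Blyth–Still–Casella method will be summarized overall and by tumor type cohort", with osteosarcoma excepted and summarized by CBRR. Pooling of the two stages is implied by these three statements rather than said outright. Neither Section 6.6 nor Section 6.8 gives a two-stage estimate, a two-stage interval or a separate summary of expansion patients.

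**The concern.** The Blyth–Still–Casella interval is exact for a single binomial sample of fixed size. A cohort that expands after a responder gate is not such a sample, because its first-stage patients are there on condition that enough of them responded. In every Table 3 row the gate sits at least 10 points above the historical rate (2/10 = 20% against 10%; 1/6 = 16.7% against 5%; 10/14 = 71.4% against 60%). Those first-stage results are carried unadjusted into the final rate.

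ORR is a named primary efficacy endpoint and is presented by cohort. Readers will look most closely at the expanded cohorts. If the drug adds nothing beyond the historical rate, the planned summary leans towards activity in exactly those cohorts, and the label on the interval suggests a precision it does not have once a cohort is known to have expanded.

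**Working it through.** **Inputs.** First-stage size n1, minimum responders r and historical rate p0 come from Table 3. The total cohort size N is an assumption. The documents fix only the cap of 40, so N = 20 and N = 40 are shown. The gate is assumed to be applied exactly at n1.

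**The plan's own figures.** Table 3 gives no formula, alpha, power or target rate, so it cannot be derived from stated inputs. An inferred rule, r = n1 × (p0 + 0.10) rounded up, matches all 11 rows. The chance of passing the gate at the historical rate is 26.3% to 33.5%.

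**Formula.** With X1 ~ Bin(n1, p) and expansion when X1 ≥ r:

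- E[X1 | expand] = n1·p × P(Bin(n1−1, p) ≥ r−1) / P(Bin(n1, p) ≥ r)
- E[pooled rate | expand] = (E[X1 | expand] + (N−n1)·p) / N

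**2-of-10 gate, p = 10%.**

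- P(expand) = 1 − 0.9^10 − 10(0.1)(0.9^9) = 0.264.
- E[X1 | expand] = 1 × (1 − 0.9^9) / 0.264 = 0.613 / 0.264 = 2.32, a first-stage rate of 23.2%.
- Pooled at N = 20: (2.32 + 1) / 20 = 16.6%.
- Pooled at N = 40: (2.32 + 3) / 40 = 13.3%.

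**1-of-6 gate, p = 5%.**

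- P(expand) = 1 − 0.95^6 = 0.265.
- E[X1 | expand] = 0.30 / 0.265 = 1.13.
- Pooled: (1.13 + 0.70) / 20 = 9.2%, or (1.13 + 1.70) / 40 = 7.1%.

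**Average bias of the pooled rate given expansion, all gates (percentage points).**

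| Gate (historical rate) | true = historical, N=20 | true = historical, N=40 | true = historical + 20, N=20 | true = historical + 20, N=40 |
|---|---|---|---|---|
| 1/6 (5%) | +4.2 | +2.1 | +1.6 | +0.8 |
| 2/10 (10%) | +6.6 | +3.3 | +1.9 | +1.0 |
| 3/10 (18%) | +8.2 | +4.1 | +2.7 | +1.4 |
| 3/10 (20%, CBR) | +7.5 | +3.7 | +2.3 | +1.2 |
| 6/12 (40%) | +9.5 | +4.7 | +2.5 | +1.3 |
| 10/14 (60%) | +11.1 | +5.5 | +2.0 | +1.0 |

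**Interval coverage given expansion.** This was found by enumerating (X1, X2) with a numerically built Blyth–Still–Casella interval. At the historical rate, coverage is 85.7% for the 2-of-10 gate at N = 20. At N = 40 it ranges from 89.1% (1-of-6 gate) to 95.5%. All or almost all misses have the lower limit above the true rate. With the true rate 20 points higher, coverage is 96% to 98%.

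**Counting stopped and expanded cohorts together.**

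- 2-of-10 gate, N = 20: the chance of expanding and then having a lower limit above 10% is 0.264 × (1 − 0.857) = 3.8%. For an ungated sample of 20 the lower limit passes 10% from 5 responders up, and P(Bin(20, 0.10) ≥ 5) = 4.3%.
- 1-of-6 gate, N = 40: 0.265 × 0.109 = 2.9%, against P(Bin(40, 0.05) ≥ 5) = 4.8% ungated.

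A cohort that stops below its gate in these examples cannot have a lower limit above the historical rate, so the gate adds no error of this kind.

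**The case against.** The study is descriptive: Section 6.1 plans no formal hypothesis test, and Section 6.8.2 calls the study hypothesis-generating. Over all cohorts, stopped and expanded, the reported rate is biased downward, by 0.7 to 4.8 points in the scenarios tried. Coverage without conditioning on expansion is mostly near or above 95%, with a lowest value of 92%. If the drug works well the upward bias is about a point at N = 40. All of this stands, and it limits the size of the point. It does not remove it, because results are presented cohort by cohort and a reader of an expanded cohort's result knows that it expanded.

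Four stronger readings are tempting, and the documents do not support them:

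- **Every expanded cohort is overstated.** The bias is an average. At N = 40 and the historical rate, the pooled rate is above the truth in 55–75% of expansions and below it in 14–29%. At 20 points higher, it is above in 46–53% and below in 34–48%.
- **Type I error is breached.** No test is planned, and the last step of the working shows no inflation at the historical rate.
- **Expanded cohorts will be formally compared with historical rates and declared active.** Historical rates are used only to set the gate.
- **Expansion happens only through the gate.** Section 3.1.2 allows exceptions. Table 3 sizes are minimums, and closing enrollment during the look is optional, so extra patients before the look would dilute the bias.

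**Conclusion.** The point holds as a weakness in estimation and reporting. Given expansion, the pooled rate is too high on average: about 2 to 6 points at N = 40 and 4 to 11 at N = 20 if the true rate equals the historical rate, and about 1 to 3 points if it is 20 points higher. The fixed-sample interval can cover less than 95% of the time near the historical rate (about 86% for 2 of 10 at N = 20, 89% for 1 of 6 at N = 40), and it errs on the optimistic side.

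These figures assume a gate applied at the Table 3 minimum size, the stated values of N, and pooling of both stages as Sections 6, 6.6 and 6.6.1 imply. Osteosarcoma shows the same effect in CBRR, although the plan names no interval method for it.

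**What to change.** In Section 6.6.1, add for each expanded cohort the ORR (CBRR for osteosarcoma) and 95% CI in expansion-stage patients alone, shown beside the first-stage and pooled results. Define expansion-stage patients as those enrolled after the data used for the initial response assessment. State that the pooled estimate and CI do not account for the response-based expansion gate.

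An alternative is to add an estimate that uses both stages and is unbiased given expansion. The plan must then say that inference is conditional on expansion, because the two standard corrections move in opposite directions. With 6 responders in 40 after a 2-of-10 gate, the pooled rate is 15.0%, the estimate unbiased given expansion is 12.1%, and the estimate unbiased over the whole design is 23.8%.

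The cost is one table row per expanded cohort. The drawback is width: using Clopper–Pearson limits for illustration, an observed 20% has a CI of 2.5–55.6% in 10 patients against 5.7–43.7% in 20. The expansion-only row should therefore sit beside the pooled result and not replace it. It also depends on a clear stage boundary, which is why the definition matters if enrollment stays open during the look.

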6.6.2 Secondary Efficacy Endpoints

The secondary efficacy endpoints include DOR and OS.

For patients who achieve an objective response, DOR is defined as the time from the first tumor assessment that supports the patient's objective response to the time of progressive disease, as determined by the investigator using *mINRC* for patients with neuroblastoma (see [Appendix 3](#)), Revised Response Criteria for Malignant Lymphoma for patients with Hodgkin's lymphoma or non-Hodgkin's lymphoma (see [Appendix 4](#)), *RANO criteria* (see [Appendix 11](#)) for patients with ATRT, and RECIST v1.1 for patients with other solid tumors (see [Appendix 6](#)), or death from any cause, whichever occurs first. The censoring method for DOR will be the same as that for PFS. The Kaplan-Meier approach will be used to estimate median DOR. The 95% CI of the median DOR will be estimated using the Brookmeyer and Crowley method. Subgroup analysis of DOR by tumor type cohort will be conducted as appropriate.

OS is defined as the time from initiation of study drug to death from any cause. Patients who are alive at the data cutoff date will be censored at the date the patient was last known to be alive. Patients with no post-baseline information will be censored at the date of initiation of study drug. The Kaplan-Meier approach will be used to estimate median OS. The 95% CI of the median OS will be estimated using the Brookmeyer and Crowley method. Subgroup analysis of OS by tumor type cohort will be conducted as appropriate.

In addition, analyses for ORR, PFS, and DOR using irRC for patients with neuroblastoma, Hodgkin's lymphoma or non-Hodgkin's lymphoma, and immune-modified RECIST v1.1 for patients with other solid tumors will be conducted with the same approaches as explained above.

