- ORR, PFS, and DOR as determined by the investigator using immune-modified RECIST v1.1 for patients with other solid tumors (see [Appendix 5](#)) and immune-related response criteria (irRC) for patients with neuroblastoma, Hodgkin's lymphoma or non-Hodgkin's lymphoma

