4.4.2 Prohibited Therapy

Use of the following therapies is prohibited during the study:

- Any concomitant therapy intended for the treatment of solid tumors, either approved by health authorities or experimental, including chemotherapy, radiotherapy (except palliative radiotherapy), hormonal therapy, immunotherapy, biologic therapy, or herbal therapy

Patients with rhabdoid tumor and ATRT may receive local therapy (radiation or surgery) after at least four cycles of atezolizumab with approval of the Medical Monitor.
- Traditional herbal or homeopathic or natural medicines

Ingredients for such medicines have not been fully studied, and their use may result in unanticipated drug-drug interactions that may cause or confound assessment of toxicity.
- Immunostimulatory agents, including but not limited to interferon (IFN)- α , IFN- γ , anti-TNF- α , or IL-2 (prohibited during the study and for 10 weeks after the last dose of atezolizumab)

These agents, in combination with atezolizumab, could potentially increase the risk for autoimmune conditions.
- Immunosuppressive medications, including but not limited to cyclophosphamide, azathioprine, methotrexate, and thalidomide

These agents could potentially alter the activity and the safety of atezolizumab.
- Live vaccines and live attenuated vaccines (prohibited during the study and for 5 months after the last dose of study drug)

Initiation of granulocyte colony-stimulating factors (e.g., granulocyte colony-stimulating factor, granulocyte/macrophage colony-stimulating factor, and/or pegfilgrastim) should be discussed with the Medical Monitor.

Systemic corticosteroids may attenuate potential beneficial immunologic effects of treatment with atezolizumab but may be administered at the discretion of the treating physician after consultation with the Medical Monitor, as described in Section 5.1.1.2.

Patients with ATRT can be receiving concurrent treatment with corticosteroids with approval from the Medical Monitor. Patients must be receiving a stable or decreasing dose for ≥ 5 days prior to the baseline MRI scan and at the time of drug initiation. The Medical Monitor should be informed when steroid doses are increased because of declining patient status.

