4.5.5.2 Response Criteria

All tumors will be evaluated for disease response and progressive disease with RECIST v1.1 (see [Appendix 6](#)) with the exception of those listed below.

- Neuroblastoma: *m*INRC (see [Appendix 3](#))
- Hodgkin's lymphoma and non-Hodgkin's lymphoma: Revised Response Criteria for Malignant Lymphoma (see [Appendix 4](#))
- ATRT: RANO criteria (see [Appendix 11](#))

Patients with synchronous ATRT and rhabdoid tumor with no clear primary should be enrolled into the rhabdoid tumor cohort. These patients' tumors will be evaluated with RECIST v1.1 criteria.

Patients who enroll with evaluable but not measurable disease will have a modified response assessment. For such patients, partial response cannot be determined; therefore, response will be limited to complete response, stable disease, or progressive disease.

During treatment, patients who show evidence of clinical benefit will be permitted to continue atezolizumab treatment after criteria for progressive disease for their specified response assessment are met, if they meet all of the following criteria:

- Evidence of clinical benefit as assessed by the investigator and agreed upon by the Medical Monitor
- Absence of symptoms or signs (including worsening laboratory test values) indicating unequivocal progression of disease
- No decline in Lansky or Karnofsky Performance Status that can be attributed to disease progression
- Absence of tumor progression at critical anatomical sites (e.g., leptomeningeal disease) that cannot be managed by protocol-allowed medical interventions

Patients and/or their parents or guardians must sign a consent acknowledging treatment continuation after possible worsening disease in order to continue to receive atezolizumab. Patients for whom radiographic disease progression is confirmed at a subsequent tumor assessment may be considered for continued study treatment at the discretion of the investigator if they have evidence of clinical benefit and continue to meet the criteria above. If an individual patient continues to experience clinical benefit beyond 2 years of radiologic progressive disease (see Section 3.3.4), the Sponsor and treating physician will apply for additional approval from health authorities for continued treatment.

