Appendix 5 Modified Response Evaluation Criteria in Solid Tumors

Conventional response criteria may not be adequate to characterize the anti-tumor activity of immunotherapeutic agents like atezolizumab, which can produce delayed responses that may be preceded by initial apparent radiological progression, including the appearance of new lesions. Therefore, modified response criteria have been developed that account for the possible appearance of new lesions and allow radiological progression to be confirmed at a subsequent assessment.

Modified Response Evaluation Criteria in Solid Tumors (RECIST) is derived from RECIST, Version 1.1 (v1.1) conventions¹ and immune-related response criteria² (irRC). When not otherwise specified, RECIST v1.1 conventions will apply.

Modified RECIST and RECIST v1.1: Summary of Changes

	RECIST v1.1	Modified RECIST
New lesions after baseline	Define progression	New measurable lesions are added into the total tumor burden and followed.
Non-target lesions	May contribute to the designation of overall progression	Contribute only in the assessment of a complete response
Radiographic progression	First instance of $\geq 20\%$ increase in the sum of diameters or unequivocal progression in non-target disease	Determined only on the basis of measurable disease

RECIST=Response Evaluation Criteria in Solid Tumors.

A. DEFINITIONS OF MEASURABLE/NON-MEASURABLE LESIONS

All measurable and non-measurable lesions should be assessed at Screening and at the protocol-specified tumor assessment timepoints. Additional assessments may be performed, as clinically indicated for suspicion of progression.

¹ Eisenhauer et al. Eur J Cancer 2009;45: 228–47; Topalian et al. N Engl J Med 2012;366:2443–54; and Wolchok et al., Clin Can Res 2009;15:7412–20.

² Wolchok et al. Clin Can Res 2009;15:7412–20; Nishino et al. J Immunother Can 2014;2:17; Nishino et al. Clin Can Res 2013;19:3936–43.

Appendix 5

Modified Response Evaluation Criteria in Solid Tumors (cont.)

A.1 MEASURABLE LESIONS

Tumor Lesions. Tumor lesions must be accurately measured in at least one dimension (longest diameter in the plane of measurement is to be recorded) with a minimum size as follows:

- 10 mm by computed tomography (CT) or magnetic resonance imaging (MRI) scan (CT/MRI scan slice thickness/interval no greater than 5 mm)
- 10-mm caliper measurement by clinical examination (lesions that cannot be accurately measured with calipers should be recorded as non-measurable)

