Partial response	
Requires all of the following:
 
 • $\geq 50\%$ decrease compared with baseline in the sum of products of perpendicular diameters of all measurable enhancing lesions sustained for at least 4 weeks • No progression of non-measurable T1 enhancing disease • No new lesions • Stable or improved non-enhancing (T2/FLAIR) lesions on the same or lower dose of corticosteroids compared to baseline • Clinical status is stable or improved 
Note: Patients with non-measurable disease only cannot have a partial response; the best response possible is stable disease

Stable disease	
Requires all of the following:
 
 • Patient does not qualify for complete response, partial response, or progression • Stable non-enhancing (T2/FLAIR) lesions on same or lower dose of corticosteroids compared to baseline • Clinical status is stable or improved 
Note: In the event that the corticosteroid dose was increased for new symptoms and signs without confirmation of disease progression on neuroimaging, and subsequent follow-up imaging shows that this increase in corticosteroids was required because of disease progression, the last scan considered to show stable disease will be the scan obtained when the corticosteroid dose was equivalent to the baseline dose.

FLAIR = fluid-attenuated inversion recovery.

Note: Adapted from Wen PY, Macdonald DR, Reardon DA, et al. Updated response assessment criteria for high-grade gliomas: response assessment in neuro-oncology working group. *J Clin Oncol* 2012;28:1963–72.

Appendix 11

Response Assessment in Neuro-Oncology Criteria (cont.)

Response	Criteria

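### The immune-modified ORR, PFS and DOR do not say which criterion applies to ATRT; read literally, it is modified RECIST, which lacks RANO's steroid, T2/FLAIR and clinical-status rules

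*Combined protocol and SAP*

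**What the plan says.** For the conventional endpoints the assignment is explicit. Section 4.5.5.2 lists "ATRT: RANO criteria" among the exceptions to RECIST v1.1, and Sections 3.4.4, 6.6.1 and 6.6.2 repeat this for objective response, PFS and DOR.

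For the immune-modified versions of ORR, PFS and DOR there are only two groups. Neuroblastoma, Hodgkin's and non-Hodgkin's lymphoma use irRC. For everything else, Section 3.4.4 has the outcomes "determined by the investigator using immune-modified RECIST v1.1 for patients with other solid tumors", and Section 6.6.2 says that analyses under "immune-modified RECIST v1.1 for patients with other solid tumors will be conducted with the same approaches as explained above". The synopsis matches. None of the three names ATRT, and no immune-adapted form of RANO appears in the documents.

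The same category is used differently in the DOR paragraph of Section 6.6.2, which gives RANO "for patients with ATRT, and RECIST v1.1 for patients with other solid tumors". There the category excludes ATRT. Section 3.1 follows the same pattern.

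Appendix 5 states that radiographic progression is "Determined only on the basis of measurable disease". Appendix 11 requires, for a partial response, "Stable or improved non-enhancing (T2/FLAIR) lesions on the same or lower dose of corticosteroids compared to baseline". Section 4.4.2 allows ATRT patients to be on corticosteroids with approval and foresees increases: "The Medical Monitor should be informed when steroid doses are increased because of declining patient status".

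**The concern.** In the immune-modified sentences the residual category contrasts only with neuroblastoma and lymphoma, so the natural reading places ATRT under Appendix 5. Those criteria were written for tumors outside the CNS. They do not ask whether the steroid dose rose between scans, whether T2/FLAIR signal worsened or whether the patient deteriorated neurologically. RANO asks all three.

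Steroid exposure in this cohort is foreseeable. Patients may enter on corticosteroids, Section 4.4.2 anticipates increases, and Section 5.1.1.4 names steroids for treatment-related raised intracranial pressure. A fall in enhancement that follows a dose increase could then be scored as a response, and clinical or T2/FLAIR worsening would not be scored as progression.

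On the other reading, ATRT has no criterion for three secondary outcomes. The choice would then be made later, in an open-label study with investigator-assessed response.

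**Working it through.** **Step 1: the two sets of rules.**

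| Rule | Appendix 5 (modified RECIST) | Appendix 11 (RANO) |
|---|---|---|
| Progression by size | +20% in sum of diameters and at least 5 mm | +25% in sum of products, on stable or increasing steroids |
| Partial response by size | -30% in sum of diameters | -50% in sum of products |
| Steroids | no rule | CR: off, or replacement doses only; PR: same dose as baseline or lower |
| T2/FLAIR | no rule | stable or improved for response; significant increase is progression |
| Clinical status | no rule; the RECIST fallback treats symptomatic deterioration as a reason to stop, not a response category | stable or improved for response; clear deterioration is progression |
| Non-measurable disease | bears on CR only; leptomeningeal disease is non-measurable | clear progression counts |
| New lesions | added to the sum; not progression alone | progression; none allowed for response |

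Appendix 5 makes the last two changes by design for every solid tumor. The gaps specific to ATRT are steroids, T2/FLAIR and clinical status.

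**Step 2: reproduce the plan's own conversion.** Appendix 6 equates a 20% increase in diameter with a 73% increase in volume. 1.20³ - 1 = 0.728, so the figure reproduces. The steps below use the same geometry (proportional change in all dimensions).

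**Step 3: progression thresholds.** Appendix 5: 1.20² - 1 = +44% in area. RANO: +25% in area, or √1.25 - 1 = +11.8% in diameter. Growth of 25% to 44% in area is progression under RANO and stable under Appendix 5. The 5 mm minimum widens the gap when the nadir sum is below 5/0.20 = 25 mm. At 15 mm, progression needs 5/15 = 33% in diameter, or (20/15)² - 1 = +78% in area.

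**Step 4: what the size threshold alone does to timing.** In volume, the thresholds are 1.20³ = 1.728 and 1.25^1.5 = 1.398. The difference is log2(1.728/1.398) = 0.31 volume doubling times. The documents give no growth rate. With an assumed doubling time of 2 to 8 weeks, the delay is 0.6 to 2.4 weeks, less than the 6 weeks between scans (two 3-week cycles) through Cycle 8.

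**Step 5: response thresholds.** Appendix 5: 0.70² - 1 = -51% in area. RANO: -50%. These are practically equal. Any excess ORR must come from patients who meet the shrinkage threshold but fail RANO on steroids, T2/FLAIR, clinical status, new lesions or non-measurable disease. The documents give no rate for this.

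**Step 6: scale of one patient.** Table 3 sets an ATRT minimum of 6, and the cohort maximum is 40. One reclassified patient moves the cohort ORR by 1/6 = 16.7 points or 1/40 = 2.5 points, and the overall ORR by about 1/100 = 1 point. This is granularity, not an estimate of bias.

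**The case against.** The strongest case against has four parts.

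- **The assignment is not certain.** Within Section 6.6.2 itself, the DOR definition uses the residual category to exclude ATRT. On that usage no ATRT result under modified RECIST is ever produced. This stands: a reader might infer that ATRT is definitely scored by Appendix 5, and the documents support that only as the more natural of two readings. It does not rescue the plan, because the other reading leaves three outcomes without a criterion.
- **A more permissive result is the purpose of an immune-modified analysis.** New-lesion and non-target progression are dropped for all solid tumors, and Section 5.1 names CNS pseudoprogression as a concern in ATRT. This also stands for those two rules. It does not explain losing the steroid, T2/FLAIR and clinical-status rules, which have nothing to do with immune response patterns.
- **The result need not be more favorable.** Response thresholds match, responses must be confirmed at least 4 weeks apart, and the steroid dose must be stable or falling before the baseline MRI and at drug initiation. Death remains a PFS event. RANO's size criterion also requires a stable or increasing steroid dose, so during a taper Appendix 5 could call progression that RANO would not. A reader might infer that the ATRT secondary result is too favorable by a known amount; the documents do not support that.
- **Little depends on it.** No hypothesis is tested (Section 6.1), and the RANO results are reported alongside. This limits the weight of the point but does not remove it.

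**Conclusion.** The plan leaves the immune-modified criterion for ATRT unstated, and its most natural reading applies criteria without the steroid, T2/FLAIR and clinical-status rules that it requires for every conventional ATRT response endpoint. Against RANO, the likely direction is later PFS and DOR events. A higher ORR is possible but less well supported. The size cannot be derived, because the documents give no growth rate, progression pattern or frequency of steroid increases. The area comparisons assume proportional change, and the 0.6 to 2.4 weeks rests on an assumed doubling time and covers the size threshold only.

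Primary ORR and PFS, conventional DOR and the Table 3 expansion rule use RANO for ATRT, and OS needs no response criterion; all are unaffected. Patients with synchronous ATRT and rhabdoid tumor are expressly assigned RECIST v1.1 in Section 4.5.5.2, which is a stated choice and outside this point. The change should be made, but the primary results do not depend on it.

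**What to change.** In the synopsis, Section 3.4.4 and Section 6.6.2, take ATRT out of the residual solid-tumor category and choose one of two options.

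1. **Analyse ATRT with Appendix 11 in the immune-modified analyses.** Keep its steroid, T2/FLAIR, clinical and non-measurable rules. Require confirmation only for radiographic progression from new or growing enhancing lesions, in line with the recommendation in Section 3.3.4. State that progression with no later scan counts at the first date, and whether RANO's bar on new lesions for a response is relaxed.
2. **Exclude ATRT from the immune-modified analyses** and report it under RANO only.

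Either option closes the gap. RANO readings are already needed for the primary endpoints. The second option costs a sentence in each place. The first costs a few sentences and a little extra analysis, and some ATRT progressions will have no confirming scan, because Section 4.5.5.1 requires the two-cycle follow-up scan only in patients treated beyond progression.
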